9.2.2. Serious, Unexpected, Suspected Adverse Reactions

In accordance with regulatory requirements, the Sponsor or designee will notify regulatory authorities as required per local law (i.e., 21 CFR 312.32 in the United States). The Sponsor or designee will also notify the Investigators, who will in turn notify their IRB as necessary, of any AE associated with study treatment administration or study procedures that is a serious, unexpected, suspected adverse reaction (SUSAR) or any finding from tests in laboratory animals that suggests a significant risk for human patients, including reports of mutagenicity, teratogenicity, or carcinogenicity. An AE or suspected adverse reaction is considered “unexpected” if it is not listed in the Investigator’s Brochure or is not listed at the specificity or severity that has been previously observed.

9.3. Adverse Events of Special Interest

Adverse events of special interest (AESIs) (serious or nonserious) are a subset of events to monitor scientific and medical concern, for which ongoing monitoring by the Investigator to the Sponsor is required. An AESI may warrant further investigation and reporting in accordance with local regulatory requirements.

Adverse events of special interest for SYNB1891 are as follows:

- Cytokine release syndrome (may include associated AEs, e.g., fever, tachypnea, headache, tachycardia, hypotension, rash, hypoxia) graded in accordance with NCI CTCAE, version 5.0
- Systemic infection (Grade 3 or higher in accordance with NCI CTCAE, version 5.0)
- Local injection site reactions (Grade 3 or higher; may include associated AEs, e.g., abscess, infection, ulceration or necrosis, or severe tissue damage) graded in accordance with NCI CTCAE, version 5.0

9.4. Reporting of Adverse Events

All AEs, serious and nonserious, will be fully documented on the appropriate eCRF. For each AE, the Investigator must provide its duration (start and end dates or ongoing), intensity, assessment of causality, and whether specific action or therapy was required.

All AEs occurring from the time a patient signs informed consent through the Safety Follow-up visit must be recorded on the eCRF.

All SAEs, regardless of relationship to study treatment, must be reported to the Sponsor within 24 hours of the Investigator's knowledge. This should be done by faxing the completed SAE Report Form to the Sponsor at the number provided on the SAE Report Form. After the Safety Follow-up visit, only SAEs that are considered related to study treatment will be recorded, if clinically indicated.

Investigators must follow patients with AEs/SAEs until event resolution or stabilization, withdrawal of consent, patient loss to follow-up, or death, whichever occurs first.

9.5. Pregnancy

If a patient becomes pregnant during the study, study treatment administration is to be discontinued immediately.

Pregnancies (both those of female patients and female partners of male patients) must be reported to the Sponsor or designee within 24 hours of the Investigator's knowledge using the designated pregnancy reporting form. Investigators should make every effort to obtain permission to follow and report the outcome of the pregnancy to the Sponsor.

Pregnancies themselves are not considered AEs or SAEs. However, any AEs or SAEs occurring during pregnancy (or the outcome of the pregnancy) are to be reported following AE and SAE reporting guidelines.

9.6. Clinical Laboratory Abnormalities

It is the responsibility of the Investigator to assess the clinical significance of all abnormal laboratory values as defined by the appropriate reference ranges. All abnormal values assessed to be of clinical concern and at least possibly related to study treatment or of uncertain causality should be repeated. Persistent abnormal values and changes of possible clinical concern that remain within the normal range should be followed at the discretion of the Investigator.

An abnormal laboratory value that is not already associated with an AE is to be recorded as an AE if an action on study treatment dosing is made as a result of the abnormality, if intervention for management of the abnormality is required, or at the discretion of the Investigator.

9.7. Review of Safety Data

The Sponsor Medical Monitor in collaboration with the CRO Medical Monitor will be responsible for the ongoing review and evaluation of safety data, including AEs, clinical laboratory data, and any other safety evaluations, for the duration of the study.

The Sponsor will host Investigator teleconferences on a regular basis during the study. In addition, the Safety Review Committee (SRC; consisting of the Sponsor Medical Monitor, the CRO Medical Monitor, all active Investigators, and other study personnel as needed) will convene when all patients have completed the first cycle of study treatment in a given cohort and review all available safety information, including DLTs and all NCI CTCAE Grade 2 or higher toxicity data, as well as any other (e.g., PK/PD) data as indicated. Updated safety data on other ongoing patients, including data from later cycles, will be discussed as well.

10. STATISTICAL METHODS AND DETERMINATION OF SAMPLE SIZE

All evaluations and tabulations will be carried out as described in detail in a statistical analysis plan (SAP), which will be finalized and approved prior to database lock.

10.1. Populations for Analysis

The following populations will be defined:

- The safety population includes participants who were enrolled, allocated to treatment, and received at least one dose of investigational product.
- The efficacy population includes participants who received study drug and had an on-treatment response assessment (including “Not Evaluable”) or who discontinued study before any response assessment was performed due to disease progression.
- The PK/PD population includes participants who received study drug and had at least one PK or PD assessment.

Additional populations may be defined in the SAP, as required.

10.2. Safety Variables

Patients in the safety population will be included in safety analyses.

Adverse events will be coded using the Medical Dictionary for Regulatory Activities (MedDRA), and the severity of AEs and laboratory abnormalities will be graded using the NCI CTCAE, version 5.0 ([US DHHS 2017](#)). AEs will be tabulated by system organ class (SOC) and preferred term. Incidence tables of patients with AEs, SAEs, and DLTs will be presented by maximum severity.

Clinical laboratory data, ECGs, and other safety assessments will be presented in by-patient listings and will be presented in tabular format, including absolute values and changes from baseline (if applicable), by dose cohort, cycle, and study day.

10.3. Efficacy Variables

Efficacy analyses will be descriptive in nature. The response of SYNB1891-injected lesion(s) and an overall response of up to 5 noninjected target lesions will be assessed. Exploratory evaluations for proof-of-concept (biopsy-based PD markers) will include change from baseline assessment.

The duration of any response or lack of progression for all evaluated tumors will also be assessed using RECIST 1.1 ([Eisenhauer et al 2009](#) and [Appendix 1](#)), iRECIST ([Seymour et al 2017](#) and [Appendix 2](#)), and/or LYRIC ([Cheson et al 2016](#) and [Appendix 3](#)).

Results will be presented in by-patient listings and will be presented in tabular format, including absolute values and changes from baseline (if applicable), by dose cohort, cycle, and study day.

10.4. Pharmacodynamic Variables

Pharmacodynamic data will be presented in by-patient listings and will be presented in tabular and/or graphical format, including absolute values and changes from baseline, by dose cohort and study day.

10.5. Kinetic Variables

Kinetics of SYNB1618 will be presented in by-patient listings and will be presented in tabular format and figures by dose cohort, cycle, and study day.

10.6. Determination of Sample Size

No formal sample size calculations were performed, as the study is primarily designed for empirical evaluation of safety and tolerability in patients with advanced solid tumors or lymphoma. The anticipated sample size is approximately 70 patients, which provides for 4 to 7 dose-finding cohorts in Arm 1, 1 to 5 cohorts in Arm 2, and replacement of 1 patient per cohort, as well up to 20 additional patients enrolled at the RP2D in Arm 2 to fully characterize the safety profile of SYNB1891 in combination with atezolizumab. Additional cohorts may be required in either arm to determine the MTD/RP2D.

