4.2.3. Dose-finding with the mTPI Algorithm

In both study arms, each cohort will initially comprise 3 patients (a Sentinel patient and 2 non-Sentinel patients), with subsequent dose escalation governed by an mTPI design (Ji et al 2013).

The starting dose of SYNB1891 in the first cohort of Arm 1 will be 1×10^6 live cells and will be increased in approximately 3-fold increments in subsequent cohorts until MTD determination. If no MTD is identified, then the MTD will be considered the maximum dose at which a sufficient number of patients have been treated such that if 14 patients were administered that dose then either escalation or staying at the current dose would be recommended according to [Table 1](#). For example, if 8 patients were administered a dose level with 0 DLTs observed, even if all remaining 6 patients had a DLT, [Table 1](#) would indicate “stay at the current dose”; thus, the remaining 6 patients are not required to evaluate the MTD.

A mTPI design with a target DLT rate of approximately 30% will be applied for dose escalation and confirmation to determine the MTD/RP2D. In Arm 1, predetermined dose levels of 1×10^6 , 3×10^6 , 1×10^7 , 3×10^7 , 1×10^8 , 3×10^8 , and 1×10^9 live cells will be explored independently, with additional dose levels as necessary to determine the MTD. A de-escalation dose of 3×10^5 live cells is available if the starting dose is deemed not tolerable. All dose escalation and de-escalation decisions will be based on the occurrence of DLTs at a given dose during Cycle 1 and will be made jointly by the Investigators and the Sponsor.

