In [Table 1](#), the number of patients treated is indicated in the columns and the number of patients who experienced a DLT is indicated in the rows. Dosing decisions include escalate to the next higher dose (E), stay at the current dose (S), de-escalate to the next lower dose (D), and de-escalate to a lower dose and never test this dose again (i.e., unacceptably toxic dose; DU). During dose escalation, a minimum of 3 patients are required at each dose. Depending on accrual rate and occurrence of DLTs, 3, 4, 5 or 6 patients may be enrolled at each new dose until the last of those patients completes the Cycle 1 DLT assessment period. For example, the dose escalation rules will proceed as follows if 3 patients are enrolled: if 0 of the first 3 patients at a given dose level develops a DLT, then the dose can be escalated to the next level without further expansion. If 1 of the first 3 patients at a given dose level develops a DLT, no more than an additional 3 patients should be enrolled at this dose level until additional DLT data are available since this dose would be considered unacceptably toxic if all 3 of the additional patients experience a DLT (i.e., 4 of 6 patients). If 2 of the first 3 patients at a given dose level develop a DLT, the dose will be de-escalated to the next lower level. If 3 of the first 3 patients at a given dose level develop a DLT, this dose will be considered unacceptably toxic (i.e., the dose will be de-escalated and never re-escalated to that dose again). The same principle will be applied whether 3, 4, 5 or 6 patients are enrolled in the same dose cohort according to [Table 1](#).

Based on the mTPI design, the number of patients who are enrolled at a dose, but are not yet fully evaluable for DLT assessment, may not exceed the number of remaining patients who are at risk of developing a DLT before the dose would be considered unacceptably toxic (denoted as DU in [Table 1](#)). To determine how many more patients can be enrolled at a dose level, one can count steps in a diagonal direction (down and to the right) from the current cell to the first cell marked DU. In total, 3 to 14 patients may be enrolled at a given dose level.

Dose escalation and confirmation will end after 14 patients have been treated at any of the selected doses. The pool-adjacent-violators-algorithm (Ji et al 2013) will be used to estimate the

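### The anticipated size of about 70 allows 3 patients plus 1 replacement per cohort and nothing more at the selected dose; at 7 and 5 cohorts Arm 1 needs at least 32 to 33 against 28, and the total is 72 to 78 or more

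*Protocol*

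**What the plan says.** Section 10.6 gives "approximately 70 patients, which provides for 4 to 7 dose-finding cohorts in Arm 1, 1 to 5 cohorts in Arm 2". The total also takes in a spare-patient allowance ("and replacement of 1 patient per cohort") and an expansion of up to 20 at the RP2D. The section adds that further cohorts may be needed, and that no formal calculation was made. The synopsis, Section 5.1 and SAP III.C say the same. Figure 4 and SAP Appendix 1 give upper limits of 28 patients in Arm 1, 20 in Arm 2 and 20 in the extension.

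Section 4.2.3 sets how many patients a dose needs:

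- To pass a dose: "During dose escalation, a minimum of 3 patients are required at each dose", although "3, 4, 5 or 6 patients may be enrolled at each new dose".
- To finish: "Dose escalation and confirmation will end after 14 patients have been treated at any of the selected doses".
- A shorter route: "If no MTD is identified, then the MTD will be considered the maximum dose at which a sufficient number of patients have been treated". Sufficient means that, were 14 treated, Table 1 could only say escalate or stay. The example given begins "if 8 patients were administered a dose level with 0 DLTs observed".

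The mTPI design "will be applied for dose escalation and confirmation to determine the MTD/RP2D", and Section 4.1 runs the algorithm separately in each arm. Expansion patients enter only after the RP2D is determined.

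**The concern.** Three patients are enough to move past a dose, but Section 4.2.3 asks for more at the dose finally selected. The anticipated size appears to count every cohort at the passing number, including the one that becomes the MTD or RP2D. If so, about 70 does not provide for the full cohort range with the stated replacements. The expansion patients cannot fill the gap, because they follow the decision that the extra patients are needed to support.

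What is at stake is the enrolment figure itself. A first-in-human trial that followed its own rules through all predetermined levels would pass the Arm 1 limit in Figure 4, and on most readings the stated total as well.

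**Working it through.** **Inputs**

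- Seven predetermined Arm 1 levels (4.2.3). Arm 2 starts at the Cohort 3 level, so five of the seven levels remain. These match the 7 and 5 in 10.6.
- Initial cohort size 3 (4.2.3), 1 replacement per cohort and up to 20 in expansion (10.6).
- 14 at a dose, or the no-MTD rule (4.2.3).

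**Reproducing the plan's figure**

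7 × (3 + 1) = 28; 5 × (3 + 1) = 20; plus 20 = 68, or about 70. The 3 + 1 split is an inference, but it returns all three Figure 4 limits exactly.

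**Minimum at the selected dose when no MTD is identified**

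The 14-patient column of Table 1 was recomputed with the stated Beta(1,1) prior, 30% target and margins of 0.03, choosing the interval among (0, 0.27), (0.27, 0.33) and (0.33, 1) with the largest posterior probability per unit length. It gives stay at 6 DLTs and de-escalate at 7. With d DLTs among n patients, the rule needs d + (14 − n) ≤ 6, so n ≥ 8 + d. The smallest n is therefore 8 with no DLTs, as in the protocol's example; 7 fails.

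**Need per arm**

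With k cohorts, m patients at the selected dose, o at each other dose and r replacements per cohort:

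N = o(k − 1) + m + r·k

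For o = 3 and r = 1:

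- Arm 1, k = 7, m = 8: 18 + 8 + 7 = 33. It is 32 if a treated but replaced patient counts toward the 8.
- Arm 1, m = 14: 18 + 14 + 7 = 39 (38).
- Arm 2, k = 5, m = 3: 12 + 3 + 5 = 20.
- Arm 2, m = 8: 12 + 8 + 5 = 25 (24).
- Arm 2, m = 14: 12 + 14 + 5 = 31 (30).

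Totals at 7 and 5 cohorts, including 20 in expansion (in parentheses, replaced patients counted toward the 8 or 14):

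| At the selected dose | Arm 1 | Arm 2 | Total |
|---|---|---|---|
| As budgeted, 3 and 3 | 28 | 20 | 68 |
| 8 in Arm 1, RP2D declared with 3 | 33 (32) | 20 | 73 (72) |
| 8 in each arm | 33 (32) | 25 (24) | 78 (76) |
| 8 in Arm 1, 14 in Arm 2 | 33 | 31 | 84 |
| 14 in each arm | 39 (38) | 31 (30) | 90 (88) |

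The row with 84 applies if the no-MTD rule does not reach the RP2D and Arm 2 runs to 14. Nor is 90 a ceiling. With 6 at every other dose (o = 6), 8 in each arm gives 51 + 37 + 20 = 108, and 14 gives 57 + 43 + 20 = 120.

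**What about 70 does cover**

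- 7 and 5 cohorts, 8 at each selected dose, no replacements: 26 + 20 + 20 = 66. That leaves room for 4 replacements, not the 12 stated.
- With one replacement per cohort and K cohorts in both arms together, the total is 4K + 30 with 8 at each selected dose (70 at K = 10, 74 at 11) and 4K + 42 with 14 (70 at K = 7, 74 at 8).
- At the lower end, 4 and 1 cohorts with 8 at each: 21 + 9 + 20 = 50.

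**The case against.** **The figure is approximate and adds up.** It is described as anticipated, rests on no formal calculation, and Section 4.2.3 openly allows 3 to 14 patients at a dose. This stands in part: 68 is correctly summed. But 10.6 says that about 70 provides for the whole cohort range with replacements, and the Figure 4 limits carry no such qualifier. The reserve in 10.6 is for additional cohorts, whereas the shortfall arises within the stated 7 and 5.

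**The 8-patient rule is not shown to govern Arm 2.** This stands. The rule names only the MTD and sits beside the Arm 1 dosing text. No section sets a minimum for declaring the RP2D, and the Safety Review Committee may declare the objectives met, with the algorithm only informing it. The text also speaks of patients treated, which may include one later replaced. A reader might infer that at least 78 are needed, or that each arm is exceeded by at least 5. The documents do not support either as a floor: the lowest combined reading is 32 + 20 + 20 = 72, with Arm 2 inside its limit.

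**It is a corner case.** It takes all 12 cohorts, all 12 optional replacements and the full optional expansion. Arm 2 must also stay at least one level below the dose under evaluation in Arm 1. While Arm 1 is at its seventh level, Arm 2 can therefore have opened only four cohorts; with 8 at each selected dose that gives 33 + 21 + 20 = 74. The fifth predetermined level opens only once Arm 1 has finished with its MTD at level 7 or has gone above it. All this makes the upper end less likely, but 10.6 names that upper end as provided for.

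**Conclusion.** The concern holds as a planning shortfall at the upper end of the stated range. The anticipated size counts 3 + 1 patients in every cohort and omits the added patients at the selected dose.

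The firmest part is Arm 1. If all seven levels run with one replacement each, it needs at least 32 to 33 patients against 28, or 39 with 14 at the MTD. The total at 7 and 5 cohorts, with 8 at the Arm 1 selected dose, is 72 to 73 if the RP2D may be declared with 3 patients and 76 to 78 if the no-MTD rule also governs Arm 2. It is about 90 with 14 at each selected dose, and more if other doses enrol more than 3.

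These totals assume the full expansion of 20. Those with 8 also assume no DLTs at that dose; each DLT there adds one patient. With fewer cohorts, or few replacements, about 70 is enough.

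A reader might also infer that the trial is underpowered or that its dose-finding rules are compromised. Neither follows: no power calculation or decision rule depends on the 70. Confidence is medium, because the Arm 2 requirement depends on how Section 4.2.3 is read.

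**What to change.** In the synopsis, Section 5.1, Section 10.6, Figure 4, SAP III.C and SAP Appendix 1, do one of the following:

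- Restate the upper-end figures: Arm 1 about 33; total about 73 to 78, or about 90 with 14 at each selected dose.
- Keep about 70, and state that it allows 3 + 1 per cohort and excludes added patients at the MTD/RP2D. With those patients included and one replacement per cohort, it covers up to 10 cohorts in all with 8 at each selected dose, or up to 7 with 14.

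In either case, reconcile within Section 4.2.3 the no-MTD rule, the 14-patient end and the committee's power to declare objectives met, so that it is clear whether the no-MTD rule applies to the RP2D. A single Arm 2 figure can then be stated.

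The cost is restated numbers or one added sentence in six places, plus the clarification. Under the restated figures the size looks less favourable; the design does not change.

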10.7. Randomization and Blinding

This first-in-human, dose-finding study will be nonrandomized with open-label study treatment.

10.8. Changes in the Conduct of the Study or Planned Analysis

Only the Sponsor may modify the protocol. Amendments to the protocol will be made only after consultation and agreement between the Sponsor and the Investigator. The only exception is when the Investigator considers that a patient's safety is compromised without immediate action. In these circumstances, the Investigator should inform the Sponsor and the full IRB within 1 working day after the emergency occurred. All amendments that have an impact on patient risk or the study objectives or require revision of the informed consent document must receive approval from the IRB prior to implementation.

11. DATA RECORDING, RETENTION AND MONITORING

11.1. Case Report Forms

Data will be collected using source documents through an electronic data capture (EDC) system at the clinical site. The Investigator or designee will record data specified in the protocol using eCRFs. Changes or corrections to eCRFs will be made by the Investigator or an authorized member of the study staff according to the eCRF completion guidelines. It is expected that the site will enter all data within 5 days of a patient visit.

It is the Investigator's responsibility to ensure eCRFs are complete and accurate, regardless of whether this responsibility has been delegated in whole or in part. Following review and approval, the Investigator or designee will electronically sign and date the pages, which certifies that the Investigator has thoroughly reviewed and confirmed all data on the eCRF.

11.2. Data Retention

Data retention practices will follow International Council for Harmonisation of Technical Requirements for Pharmaceuticals for Human Use (ICH) guidelines, which note that essential documents should be retained for a minimum of 2 years after the last approval of a marketing application in an ICH region and until there are no pending or contemplated marketing applications in an ICH region or at least 2 years have elapsed since the formal discontinuation of clinical development of SYNB1891. However, these documents should be retained for a longer period if required by the applicable legal requirements.

11.3. Data Monitoring

This study will be closely monitored by representatives of the Sponsor or designee throughout its duration. Monitoring will include personal visits with the Investigator and study staff as well as appropriate communications by telephone, fax, mail, email, or use of the EDC system, as applicable. It is the monitor's responsibility to inspect eCRFs at regular intervals throughout the study to verify the completeness, accuracy, and consistency of the data and to confirm adherence to the study protocol and to Good Clinical Practice (GCP) guidelines. The Investigator agrees to cooperate with the monitor to ensure that any problems detected during the course of this study are resolved promptly. The Investigator and site will permit study-related monitoring, audits, IRB review, and regulatory inspection, including direct access to source documents.

It is understood that study monitors and any other personnel authorized by the Sponsor may contact and visit the Investigator and will be permitted to inspect all study records (including eCRFs and other pertinent data) on request, provided that patient confidentiality is maintained and that the inspection is conducted in accordance with local regulations.

Every effort will be made to maintain the anonymity and confidentiality of patients during this study. However, because of the experimental nature of SYNB1891, the Investigator agrees to allow representatives of the Sponsor and authorized representatives of regulatory authorities to inspect the facilities used in the conduct of this study and to inspect, for purposes of verification, the hospital or clinic records of all patients enrolled in the study.

